5.1.11 Unscheduled Visits

Additional visits may be performed as appropriate and at the discretion of the investigator. Any of the procedures or assessments may be performed based on the reason for the visit.

5.1.12 **Restrictions, Precautions, and Potential Adverse Effects**

There are no known restrictions or precautions relative to nicotine, caffeine, alcohol, physical activity, fasting, diet, or medications for patients' ongoing IMSA101 treatment.

Based on pre-clinical findings with IMSA101 and toxicity events reported in clinical trials evaluating other STING (stimulator of interferon genes) adapter protein agonists, the following risks may reasonably be anticipated in clinical trials evaluating IMSA101: body temperature increases (fever), chills, alterations in serum chemistries, altered serum hematology parameters, headache, injection site pain, vomiting, fatigue, myalgia, and/or diarrhea.

6 METHODS OF ASSESSMENT AND ENDPOINTS

6.1 MTD/RP2D

Definition of Maximum Tolerated Dose (MTD): The MTD is defined as the highest dose level of IMSA101 at which no more than 1 out of 6 (7 when applicable) patients experiences a DLT during the first cycle (28 days) of therapy.

Definition of Recommended Phase 2 Dose (RP2D): The RP2D is defined as the dose (either at MTD or below MTD) that is selected for evaluation in the Phase IIA component of the study.

The MTD/RP2D of IMSA101 will be determined by the sponsor and the CRC.

6.2 DEMOGRAPHIC DATA

At screening, patient demographic data will be collected. These data include: year of birth, age, gender, race, smoking history, tumor type, and molecular abnormalities, if known.

6.3 MEDICAL HISTORY

At screening, a complete medical history will be obtained from each patient. Medical history includes baseline symptoms as well as a detailed history of prior procedures and prior cancer therapies including therapy start and stop dates, best response, disease progression during or after therapy, as well as discontinuations due to intolerability or toxicity. For female patients of child-bearing potential, the date of the last menstrual period should be noted. Data will be updated at subsequent visits as appropriate.

6.4 CONCOMITANT MEDICATIONS

A detailed history of medications and procedures will be documented for each patient at screening. Concurrent medications (especially changes in medication) will be documented for each patient at each scheduled visit. Necessary supportive care such as anti-emetic and antidiarrheal medications, etc., will be allowed (see Section 8.3). Prophylactic pretreatment for headache, nausea, and vomiting (after Cycle 1) is permitted. Any medication that in the opinion of the investigator will interfere with the MOA of IMSA101 is prohibited.

6.5 PHYSICAL EXAMINATION AND VITAL SIGNS

Full physical examinations will be performed at screening and End of Treatment (EOT) Visit. An assessment of interval changes and AEs will be performed at each visit.

- Height in centimeters (cm) will be measured at screening.
- Body weight in kilogram (kg) will be measured at screening/baseline, and all study visits.
- Vital signs including body temperature, blood pressure, respiration rate, and heart rate will be measured at all study visits.

Information about the physical examination must be present in the source documentation at the study site. The result of the physical examination prior to the start of study drug treatment must be included in the Relevant Medical History/Current Medical Conditions Case Report Form. Clinically relevant findings made after the start of study drug treatment, which meet the definition of an AE, must be recorded on the Adverse Event Case Report Form.

6.6 SAFETY ASSESSMENTS

Safety assessments will include TEAEs, DLTs, vital signs, 12-lead ECG, physical examination, and laboratory safety evaluations. Toxicities will be graded according to CTCAE v5.0 criteria. Patients will be observed for 1 h in the clinic following intratumoral injections. In addition, following intratumoral injection on Day 1 of Cycle 1, patients will be admitted to the hospital for observation overnight.

Safety data will be listed by study site, patient number, and cycle. All TEAEs will be summarized by study phase and assigned dose. In addition, all SAEs, including deaths will be listed separately and summarized.

Grade 3 and 4 laboratory data will be summarized by study phase and assigned dose.

For patients who experience a DLT, data on AEs leading to treatment/study discontinuation will be listed.

Coagulation and urinalysis will be performed only at screening.

Safety evaluations (vital signs, ECOG assessment, and clinical laboratory studies) will be conducted at screening, Cycle 1 Day 1; baseline, then on Days 8 and 15 of Cycle 1, then Day 1 and Day 15 of every cycle thereafter for patients who continue treatment, or any time it is clinically indicated in the judgment of the investigator.

Neurologic examinations and ECOG performance status assessments (Appendix 13.1) will be performed at each study visit.

A complete standard 12-lead ECG recording (rhythm, VR, PR interval, QRS duration, QT and QTc) will be performed at screening, 30 minutes post-dose on C1D1, C1D8, C1D15, at EOT, and at any other visit where the investigator believes the assessment is indicated.

The following clinical laboratory tests will be performed:

• **Hematology** (blood sample with EDTA): hemoglobin, hematocrit, mean corpuscular volume, mean corpuscular hemoglobin, mean corpuscular hemoglobin concentration, white blood cell (WBC) count, WBC differential, red blood cell count, lymphocytes, monocytes, neutrophils, band neutrophils, eosinophils, basophils, platelets. The WBC differential may be automated or manual as per institutional standards. Reticulocytes should be done only when clinically indicated.

- Serum Chemistry (blood serum sample): Complete Serum Chemistry will include sodium, potassium, chloride, bicarbonate, blood urea nitrogen, creatinine, glucose, calcium, phosphate, magnesium, ALT, AST, alkaline phosphatase, total bilirubin, lactate dehydrogenase, total protein, albumin.
- **Coagulation (screening only):** PT, international normalization ratio (INR), and activated partial thromboplastin time (aPTT).
- Urinalysis (screening only): appearance, color, urine bilirubin, glucose, hemoglobin, ketones, pH, protein, specific gravity, urobilinogen, and microscopy.

Any laboratory value that remains abnormal at the EOT and that is considered clinically significant will be followed according to accepted medical standards for up to 30 days after the last dose or until resolution of the abnormality.

Toxicity will be assessed using the CTCAE v5.0 criteria.

6.7 PHARMACOKINETIC PROCEDURES

6.7.1 Blood Sampling and Processing

Blood plasma samples for PK analysis will be collected from Phase I monotherapy patients at the times/days outlined below and in Table 1. Further details and instructions will be provided in a separate laboratory manual.

Cycle 1 Day 1:

Pre-Dose, 10 min, 20 min, 30 min, 1 h, 2 h, 4 h post-dose

Cycle 2 Day 15 (if any detectable signal noted in Cycle 1):

Pre-Dose, 10 min, 20 min, 30 min, 1 h, 2 h, 4 h post-dose. Additionally, 6 h, 24 h post-dose if previous 4 h post-dose measurement was found detectable in Cycle 1

The following time windows for plasma PK sample collection are allowed: ≤ 24 h for the predose sample, ± 5 min for the 10-, 20-, and 30-min post-dose samples, ± 10 min for the 1-h postdose sample, ± 15 min for the 2-, 4-, and 6-h post-dose samples, and ± 2 h for the 24-h post-dose sample.

Plasma concentrations for all PK parameters at each time point will be listed and summarized by each dose level. Plasma concentrations versus time profiles (with concentrations on both a log and linear scale) will be plotted for each patient; similar summary plots will be constructed for each dose level. PK parameters will be analyzed by a validated bioanalytical method from a central laboratory.

6.8 PHARMACODYNAMIC PROCEDURES

6.8.1 **Blood and Tissue Sampling and Processing (Phase I only)**

Blood and tumor samples are to be collected at multiple time points as shown in Section 2.4.5 and Table 1 for exploratory assessment of numerous biomarkers.

The following time windows for PD cytokines sample collection are allowed: ≤ 24 h for the predose sample, ± 15 min for the 2-, 4-, and 6-h post-dose samples, and ± 2 h for the 24-h post-dose sample.

The following time windows for PD flow cytometry sample collection are allowed: \leq 24 h for the pre-dose C1, C2, and C3 samples.

The following time windows for PD mIF sample collection are allowed: \leq 24 h for the pre-dose C1D1, C1D15, and C2D15 samples.

An aliquot of tumor sample for injected and non-injected tumor is to be obtained and stored for later RNA isolation and sequencing when the analysis is warranted based on clinical or immunological responses.

PD markers will be analyzed by a validated bioanalytical method from a central laboratory. Further details and instructions will be provided in a separate laboratory manual.

6.9 TUMOR ASSESSMENTS

All known tumor sites will be documented at screening and re-assessed at each subsequent time point for tumor evaluation, using a single and consistent methodology throughout all evaluations. Assessments may include the following:

- Screening (if a recent scan within the past month is not available in the medical records) and subsequent tumor assessments must include CT scans (with IV contrast unless contraindicated and oral contrast as appropriate per institutional standards) or MRI of the chest, abdomen, and pelvis (or other appropriate assessment). Photographic assessments of skin lesions will be performed through a photography vendor as detailed in a separate photography manual. At screening, photography assessment can be performed within 30 days prior to Day 1.
- If a CT scan is performed in a positron emission tomography/CT scanner, the CT acquisition must be consistent with the standards for a full-contrast CT scan.
- Brain imaging (by either MRI or contrast-enhanced CT) is required at screening for all patients displaying clinical signs of possible central nervous system involvement.
- Further investigations such as bone scans should be performed if there is any clinical suspicion of disease at any site that may not be observed using the methods above.

- The same radiographic procedures used to assess disease sites at screening should be used throughout the study (e.g., the same contract protocol for CT scans). Assessments should be performed by the same evaluator if possible to ensure internal consistency across visits.
- All findings will be assessed for response according to RECIST v1.1 criteria as defined in (Appendix 13.2) and according to the Schedule of Assessments and Study Activities (Table 1 and Table 2).

RECIST v1.1 criteria do not mention including or excluding lesions that are being biopsied or injected. However, for the purposes of this protocol, the injected and biopsied lesions are to be captured as non-target lesions only (Phase I only), as follows:

- Injected and biopsied lesion = non-target lesion #1
- Non-injected and biopsied lesion = non-target lesion #2 (if applicable)
- In certain circumstances a patient experiencing RECIST progression of disease may be allowed to continue therapy on study where there is agreement between the investigator and sponsor that the patient is deriving clinical benefit.

7 DISCONTINUATION CRITERIA

7.1 DISCONTINUATION OF INDIVIDUAL PATIENTS

Patients are free to withdraw from the study at any time without providing reason(s) for withdrawal and without prejudice to further treatment. The treatment of individual patient(s) may be stopped by the investigator under defined circumstances as outlined below.

- Patient request
- Use of non-permitted concurrent therapy
- Non-compliance with the study drug or study schedule
- Patient lost to follow-up
- Occurrence of AEs not compatible with the continuation of patient participation in the study, in the investigator's opinion, or unacceptable to the patient to continue
- Investigator/sponsor request
- Intercurrent illness warranting removal by the investigator
- Disease progression warranting removal by the investigator

The reason(s) for withdrawal (by the patient or investigator) and date will be documented in the electronic case report form (eCRF).

All patients who withdraw from the study with an ongoing AE must be followed until the event is resolved or deemed stable. Any patient who withdraws consent as a result of an AE, regardless of intensity or investigator's opinion, must be reported as a discontinuation due to AE. Patients withdrawing from the study will be encouraged to complete the final evaluations as detailed for termination in the Schedule of Assessments (Table 1 and Table 2), particularly safety evaluations.

If a patient refuses to complete early termination procedures, this information will be recorded in the source documentation. A patient who prematurely discontinues from the study for any reason will not be allowed to re-enter the study.

In certain circumstances, a patient experiencing RECIST progression of disease may be allowed to continue therapy on study where there is agreement between the investigator and sponsor that the patient is deriving clinical benefit.

7.2 EARLY DISCONTINUATION OF THE STUDY

The sponsor has the right to terminate the study at any time in case of SAEs or if special circumstances concerning the IMSA101 or the company itself occur, making further treatment of patients impossible. In this event, the investigator(s) will be informed of the reason for study termination.

In particular cases, the study may be terminated at a single study site at any time if it becomes apparent that patient enrolment or quality of the data is unsatisfactory, or the conduct of the study at this site is not in accordance with the Good Clinical Practice (GCP) guidelines.

Study materials must be returned, disposed of or retained as directed by the sponsor.

8 TREATMENT

8.1 DOSING AND ADMINISTRATION OF IMSA101

IMSA101 is a sterile, nonpyrogenic solution containing 10 mg of IMSA101 in 1.0 mL of Prior to dosing, IMSA101 will be thawed and further diluted in order to be delivered intratumorally at the following dose levels:

Monotherapy: 100, 200, 400, 800, and 1,200 µg.

Combination Therapy IMSA101 + current ICI therapy (administered according to the label of that product):

- 800 and 1,200 µg
- 2,400 µg (with an initial "priming" dose of 1,200 µg)
- 3,600 µg (with an initial "priming" dose of 2,400 µg)
- 4,800 µg (with an initial "priming" dose of 3,600 µg)

This drug is **NOT SAFE** to be administered without proper dilution. Composition of IMSA101 is presented in Table 4.

Table 4Composition of IMSA101 for Injection

Ingredients	Grade	Function	Composition (1.2 mL per vial)

NF: National Formulary; USP: United States Pharmacopeia

8.1.1 **Preparation of IMSA101**

Prior to dosing, IMSA101 will be thawed and diluted **sectors** as detailed in a separate pharmacy manual. A single pre-defined tumor/tumor site per patient will be selected and injected intratumorally throughout study participation. Injections of tumors that are not superficial will be performed under image guidance.

8.1.2 Administration of IMSA101

Phase I (dose escalation):

For monotherapy, IMSA101 will be administered at dose levels of (but not necessarily be limited to) 100, 200, 400, 800, and 1,200 μ g (Table 5). One mL total volume will be administered each week for 3 weeks in Cycle 1 (Days 1, 8, and 15). For Cycle 2 and all other cycles thereafter, study drug will be given by intratumoral injection every other week on Days 1 and 15.

For combination therapy, IMSA101 will be administered at dose levels of 800 and 1,200 µg. One mL total volume will be administered each week for 3 weeks in Cycle 1 (Days 1, 8, and 15). For Cycle 2 and all other cycles thereafter, study drug will be given by intratumoral injection every other week on Days 1 and 15. Additional combination therapy dose levels of 2,400, 3,600, and 4,800 µg require the following priming dose on Day 1 of Cycle 1: 1,200 µg for the 2,400 µg dose, 2,400 µg for the 3,600 µg dose, and 3,600 µg for the 4,800 µg dose. After Day 1 of Cycle 1, the full dose for these groups will be administered on Day 1 of Weeks 2 and 3 of Cycle 1 (i.e., weekly dosing 3 out of 4 weeks), and on Day 1 of Weeks 1 and 3 for all cycles thereafter (i.e., bi-weekly dosing).

IMSA101 is injected directly into the selected tumor. Patients will be observed for 1 h following each intratumoral injection. In addition, following intratumoral injection on Day 1 of Cycle 1, patients will be admitted to the hospital for observation overnight.

Injectable tumors shall be accessed by intralesional (cutaneous) or percutaneous injection only, including those lesions that are visible, palpable, or detectable by standard radiographic or ultrasound methods. The administration technique and procedures for internal lesions (i.e., whether CT or ultrasound guided) will be per institutional policy and guidelines. Neither surgical procedures nor endoscopically-guided injections including those to endobronchial, endoluminal, or endosinusoidal spaces shall be allowed. While no anatomic locations are required or disallowed, lesions selected for intratumoral injection must, in the opinion of the investigator:

- Not be immediately adjacent to blood vasculature or other physiologic landmarks in such a way that will accrue undue safety risk to the patient
- Have longest diameter $\geq 10 \text{ mm and} \leq 50 \text{ mm}$
- Be fully efficacy evaluable per RECIST v1.1 criteria (Appendix 13.2)

Where no remaining accessible lesions are present and where benefit of IMSA101 therapy is, in the opinion of the investigator, being derived by the patient, continued injections of IMSA101 into the vicinity of an inaccessible lesion shall be allowed. In the case that a lesion can no longer be radiographically visualized, continued injections into the last known location of the non-visible lesion shall be allowed.

For those patients receiving a combination regimen, the combination partner drug will be administered per product label.

Dose Level	IMSA101 Dose	
Monotherapy		
1	100 µg*	
2	200 µg	
3	400 µg	
4	800 μg	
5	1,200 µg	
	Combination Therapy	
1	800 μg	
2	1,200 µg	
3	$2,400 \ \mu g$ with an initial priming dose of $1,200 \ \mu g$	
4	$3,600 \ \mu g$ with an initial priming dose of $2,400 \ \mu g$	
5	$4,800 \ \mu g$ with an initial priming dose of $3,600 \ \mu g$	

Table 5Dose Levels of IMSA101 for Injection

* The lowest dose (100 μ g) represents 1/60th of the preclinical highest non-severe toxic dose (HNSTD). Dose escalation design in which administered dose levels will be escalated stepwise in successive cohorts of 3 to 6 (4 to 7 when applicable) patients each (standard 3+3 study design) until the MTD or RP2D level is identified.

Phase I (dose de-escalation for combination therapy):

If \geq 2 DLTs occur among the initial 3 (4 when applicable) or 6 (7 when applicable) patients, de-escalation of IMSA101 is allowed for the combination therapy dose levels as follows:

- 2,400 μg may be de-escalated to 1,800 μg (with a priming dose of 1,200 μg on Day 1 of Cycle 1)
- 3,600 μg may be de-escalated to 3,000 μg (with a priming dose of 2,400 μg on Day 1 of Cycle 1)
- 4,800 μg may be de-escalated to 4,200 μg (with a priming dose of 3,600 μg on Day 1 of Cycle 1)

If \geq 2 DLTs occur among the initial 3 (4 when applicable) or 6 (7 when applicable) patients at a de-escalated dose level, the dose level shall be considered unacceptably toxic and escalation will be discontinued.

Phase IIA (dose expansion):

IMSA101 will be given at the RP2D through intratumoral injection as described for Phase I above.

Patients will receive either IMSA101 monotherapy or in combination with IO therapy. A safety run-in component will establish safety of the combination before further patients are enrolled (Section 3.1.2).

8.2 STORAGE OF IMSA101

The drug product is packaged in a container-closure system that is composed of pharmacopoeiacompliant components. The primary container, composed of United States Pharmacopeia (USP) Type 1 glass, is stoppered with a 13 mm Fluortec coated lyophilization stopper, and sealed with a 13 mm flip-off overseal and 13 mm cap. A 24-unit paper carton is used to distribute the product to clinical sites.

The product (IMSA101 for Injection) is stored at $-20 \pm 5^{\circ}$ C and is being tested for 5 years of shelf-life through a stability protocol. Currently, the product has completed the 3-year time point for stability with all tests meeting specification. Clinical trial sites will be provided specific expiry and stability updates via memoranda as new data become available.

8.3 RESCUE MEDICATIONS AND CONCOMITANT TREATMENTS

All medications administered from the beginning of study treatment (Cycle 1 Day 1, including during the overnight hospitalization) through the end of treatment and study participation will be recorded on the eCRF. Any change in medication dosage will also be noted.

Necessary supportive care (i.e., antiemetic and/or antidiarrheal medications, etc.) will be allowed. Prophylactic pretreatment for headache, nausea, and vomiting (after Cycle 1) is permitted.

8.4 TREATMENT COMPLIANCE

The investigator and/or his study staff will administer IMSA101 study medication only for use by patients enrolled in the study as described in this protocol. The study medication is not to be used for reasons other than those described herein.

The investigator or other study staff will supervise study drug treatment given in the clinic and record all treatments in the eCRF. Study personnel associated with the sponsor will monitor IMSA101 drug treatment compliance.

9 ADVERSE EVENTS

9.1 **DEFINITIONS**

9.1.1 Adverse Event

An AE is defined as any undesired medical occurrence in a patient or clinical investigation patient receiving a pharmaceutical product and which does not necessarily have a causal relationship with this treatment. An AE can therefore be any unfavorable sign and unintended sign (including an abnormal laboratory finding), symptom, or disease temporarily associated with the use of a study drug, whether or not related to the study drug. AE reporting begins at the time of study drug administration and continues until 30 days after the last dose.

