2.4.4 Pharmacokinetic Endpoints (Phase I Monotherapy only)

• PK parameters of IMSA101 administered by intratumoral injection:

Cycle 1 Day 1: Pre-Dose, 10 min, 20 min, 30 min, 1 h, 2 h, 4 h post-dose

Cycle 2 Day 15 (if any detectable signal noted in Cycle 1):

Pre-Dose, 10 min, 20 min, 30 min, 1 h, 2 h, 4 h post-dose. Additionally, 6 h, 24 h post-dose if previous 4 h post-dose measurement was found detectable in Cycle 1

2.4.5 **Exploratory Pharmacodynamic Endpoints (Phase I only)**

- Blood levels of cytokines (pre-dose, 2h, 4h, 6h, 24 h post-dosing Cycle 1 Day 1 and Cycle 2 Day 15): IL6 and IP10, IFNγ, TNFα, IL-10, IL-1β, IFN-β, MCP-1 (CCL2)
- Blood (pre-dose on Day 1 of Cycles 1, 2, and 3): Flow cytometry of Cryopreserved PBMCs CD3, CD4, CD8, CD45, CD69, CD19, CD56, FOXP3, PD-1, PD-L1, CD141, CD86, HLA-DR, CD14, CD16, CD11c
- Tumor Biopsy for injected tumor and non-injected tumor, if applicable (non-injected tumor biopsy required in at least 1 patient per cohort) (pre-dose on Cycle 1 Day 1, Cycle 1 Day 15, Cycle 2 Day 15:) Multiplexed Immunofluorescence (mIF) including antibodies to CD45, CD4, CD8, CD11c, CD56(NK), FOXP3, DAPI, PD-1, and PD-L1

An aliquot of tumor sample for injected and non-injected tumor is to be stored for later RNA isolation and sequencing when the analysis is warranted based on clinical or immunological responses.

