- PD tissue samples/biopsy of injected and non-injected tumor, if applicable (non-injected tumor biopsy required in at least 1 patient per cohort) (Phase I monotherapy and combo therapy). Core biopsies should be obtained; if not appropriate, biopsies via fine needle aspirate (FNA) or excision are permitted. Detailed instructions outlined in the laboratory manual.
- Administer study drug(s).
- Observe patient for 1 h following intratumoral injection.
- Assess and record AEs.
- Admit patient to the hospital for observation overnight. Patient may be released from the hospital when clinically indicated.

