9.1.2 Serious Adverse Events

An SAE is any untoward medical event that occurs at any dose from the time of study drug administration and continuing until 30 days after the last dose that:

- results in death
- is life-threatening (patient is at immediate risk of death from the event as it occurred)¹
- requires inpatient hospitalization (formal admission to a hospital for medical reasons) or prolongation of existing hospitalization ²
- results in persistent or significant disability/incapacity ³
- results in a congenital anomaly/birth defect
- is an important medical event ⁴
- ¹ "Life-threatening" means that the patient was at immediate risk of death at the time of the SAE; it does not refer to a SAE that hypothetically might have caused death if it were more severe.
- ² This means that hospital inpatient admission or prolongation of hospital stay was required for the treatment of the AE, or that one or the other occurred as a consequence of the event. Hospitalizations for elective surgery or other medical procedures that are not related to a TEAE are not considered SAEs. The planned overnight hospitalization on Day 1 of Cycle 1 is exempt from this definition and is not considered an SAE since it is a study procedure and not for treatment of an SAE, unless an AE occurs during the hospitalization that meets the criteria above.
- ³ "Persistent or significant disability or incapacity" means a permanent or significant and substantial disruption of a person's ability to carry out normal life functions.
- ⁴ Important medical events that may not result in death, are not life-threatening, or do not require hospitalization may be considered SAEs when, based on appropriate medical judgment, they may jeopardize the patient and may require medical or surgical intervention to

prevent one of the outcomes listed in this definition. Examples of such events include allergic bronchospasm requiring intensive treatment in an emergency room or at home, blood dyscrasias or convulsions that do not result in inpatient hospitalization, or the development of drug dependency or drug abuse.

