9.2 SERIOUS ADVERSE EVENT REPORTING

9.2.1 **Reporting Requirements**

Any SAE made known to the investigator must be reported by the investigator if it occurs during the clinical study, whether or not the SAE is considered to be related to the IMSA101 treatment. An SAE report consists of the SAE form, the AE form, and the concomitant medication form.

A copy of these forms must be forwarded within 24 h of awareness. Contact details will be provided in the study reference manual.

The investigator should not wait to receive additional information to document fully the event before notification of an SAE, though additional information may be requested. Where applicable, information from relevant laboratory results, hospital case records, and autopsy reports should be obtained.

Instances of death, congenital abnormality, or an event that is of such clinical concern as to influence the overall assessment of safety, if brought to the attention of the investigator at any time after cessation of study drug administration and linked by the investigator to this study, should be reported to the medical monitor.

Progression of disease by itself is not considered an AE but rather an expected outcome and a study endpoint and should not be reported as AEs or SAEs, unless it results in hospitalization or death. AEs associated with progressive disease (such as a pleural effusion or gastrointestinal obstruction) and associated hospitalizations to treat the AE or SAE are reportable events.

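### Phase I complications of the Cycle 1 Day 1 biopsy that begin before the first injection, or occur in patients never dosed, fall outside AE and SAE collection

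*Combined protocol and SAP*

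**What the plan says.** The AE window is set in Section 9.1.1: "AE reporting begins at the time of study drug administration and continues until 30 days after the last dose". Table 1 footnote 12 and Table 2 footnote 10 repeat it, and neither schedule marks an AE assessment at screening. Section 9.1.2 defines an SAE as an event "that occurs at any dose from the time of study drug administration and continuing until 30 days after the last dose".

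Section 2.4.5 schedules Phase I tumour biopsies "pre-dose on Cycle 1 Day 1, Cycle 1 Day 15, Cycle 2 Day 15". The Cycle 1 Day 1 visit list in Section 5.1.2 includes "PD tissue samples/biopsy of injected and non-injected tumor, if applicable", with the non-injected lesion required in at least one patient per cohort. On method it says: "Core biopsies should be obtained; if not appropriate, biopsies via fine needle aspirate (FNA) or excision are permitted". Section 6.8.1 allows up to 24 hours "for the pre-dose C1D1, C1D15, and C2D15 samples".

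For SAE reporting, Section 9.2.1 says that any SAE "must be reported by the investigator if it occurs during the clinical study", whether or not it is thought related to treatment.

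**The concern.** The baseline biopsy is done only because the protocol asks for it, and core biopsy is the default. Section 4.2 disallows no anatomic site for the injected lesion, which is also the biopsied one. It permits percutaneous access and admits patients with platelets just above 50,000 cells/µL. A bleed, or a pneumothorax where a lung lesion is sampled, is a foreseeable complication.

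If safety collection opens only at the first injection, harm from a study procedure performed before it has no defined place in the safety data. The gap is also selective. A more severe complication is more likely to stop the patient being dosed, and a patient never dosed drops out of the safety data altogether. At stake is a complete account of the harm caused by study participation.

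**Working it through.** The plan states no figure to reproduce on this point. The check compares the start of collection with the timing of each biopsy.

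**Biopsy times (Section 2.4.5).** There are three: Cycle 1 Day 1, Cycle 1 Day 15 and Cycle 2 Day 15. All are labelled pre-dose, but only the first precedes the first dose. So 1 of 3 lies before collection opens and 3 − 1 = 2 lie inside it.

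**Length of the gap (Section 6.8.1).** It is at most 24 hours for a patient dosed as planned. It has no end for a patient who is biopsied and never dosed.

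**What happens to each kind of event:**

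| Complication | AE under 9.1.1 | SAE under 9.1.2 | In the Safety Population (10.2.1) |
|---|---|---|---|
| Cycle 1 Day 1 biopsy, starts before the first injection, patient later dosed | No | No | Patient yes, event no |
| Cycle 1 Day 1 biopsy, patient never dosed | No | No | No |
| Cycle 1 Day 1 biopsy, starts after the first injection | Yes | Yes, if serious | Yes |
| Cycle 1 Day 15 or Cycle 2 Day 15 biopsy | Yes | Yes, if serious | Yes |

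The last two rows are covered because Section 9.1.1 counts events regardless of their relation to the study drug.

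**Whether other sections close the first two rows:**

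- Section 6.5 sends findings made after the start of study drug to the AE form. The examination result from before treatment goes to the medical history form.
- Section 10.2.1 limits the Safety Population to patients with at least one dose, and Section 10.3.5 bases all safety summaries on it.
- Section 11.8.1 requires complete data collection only for patients who both consent and are treated.
- Section 9.2.1 does not say when the clinical study begins for a patient. Read alone, it could reach back before dosing. Read with Section 9.1.2, an event before dosing is not an SAE, so there is nothing to report. It does not address non-serious events.
- Table 1 footnotes 4 and 16 allow screening laboratory tests and the Cycle 1 Day 1 vital signs, neurologic examination and ECOG assessment up to 72 hours beforehand. All may therefore precede the biopsy. The next scheduled haematology is on Day 8.

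**Patients exposed.** Section 4.1 gives approximately 45 for Phase I. Table 2 has no tissue sampling row, so Phase IIA adds none.

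**The case against.** The strongest reply is that the gap is narrow. The biopsy belongs to the Cycle 1 Day 1 visit, and the injection is followed by one hour of observation and an overnight admission, all inside AE collection. A complication that shows itself after the injection is reportable whatever its cause. Section 11.3 also has the investigator notify the IRB/IEC of SAEs or other significant safety findings, and Section 6.3 records baseline symptoms and prior procedures. All of this stands, and it limits the point to onset before the injection and to patients never dosed. It does not remove the point: notification under Section 11.3 follows each committee's policy and does not feed the trial database, and a medical history entry is not a safety event.

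A reader might infer three stronger things that the documents do not support.

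- **That biopsy complications are never captured.** The two later biopsies, and any onset after the first injection, are covered.
- **That dose-limiting toxicity decisions are distorted.** Section 3.1.3 requires at least a possible relation to IMSA101. Table 7 reserves that category for events starting a reasonable time after administration, so an event with onset before dosing fails the test. Section 10.3.6 lists beginning and end times for recorded events. Misattribution is not shown.
- **That the loss can be quantified.** Assume a complication risk of 1% to 5% per patient. For 45 patients, 1 − 0.99^45 = 0.36 and 1 − 0.95^45 = 0.90. That is the chance of at least one complication with any onset, not of a missed one. If half began before the injection, a further assumption, the results are 1 − 0.995^45 = 0.20 and 1 − 0.975^45 = 0.68. Neither assumption has a source in the documents, so these figures show only how far the answer depends on the inputs.

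**Conclusion.** The concern holds in a limited form. In Phase I, complications of the Cycle 1 Day 1 biopsy that begin before the first injection, or that occur in patients biopsied but never dosed, are outside the AE and SAE windows as written. Section 9.2.1 conflicts in scope with Section 9.1.2 and does not clearly bring them back in.

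The extent is one of three biopsy time points, an interval of at most 24 hours for patients dosed as planned, and about 45 patients exposed. The number of missed events cannot be derived. The conclusion rests on the stated collection rules and needs no assumed complication rate. It is a shortfall in safety capture that is cheap to correct, and it is not shown to affect the MTD or RP2D determination.

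**What to change.** In Sections 9.1.1 and 9.1.2 and in Table 1 (the AE row and footnote 12):

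- Collect all SAEs, and AEs related to protocol-mandated procedures, from the first study-specific procedure. Section 5.1.1 already requires consent before that point.
- Apply this to consented patients who are never dosed, and adjust the data-collection rule in Section 11.8.1 to match.
- List these events separately from the safety summaries.
- Keep treatment-emergent events counted from the first dose, and write that definition down, because the documents use the term without defining it.
- Reconcile Section 9.2.1 with Section 9.1.2 so that both use the same start.

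A matching edit to Table 2 would be for consistency only, since Phase IIA has no scheduled biopsy. The cost is minor extra data entry, with no added visit or procedure.
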